9.7.2 Double-blind Month 12 and OL-500 analyses

These results were summarized using descriptive statistics and presented overall and for each age group and visit in total and by treatment group (placebo/dose level/overall active) on the SS for the randomized blinded treatment period.

These analyses were repeated overall and for each age group and visit in total and by initial actual treatment group on the OLS-500, for the Viaskin Milk 500 μ g open-label

This document is confidential

Statistical Analysis Plan

treatment period. Similarly, the last value in Viaskin Milk 500 μ g open-label treatment period were summarized.

Worst grades reported for any treatment period will also be tabulated.

9.7.3 OL-300 Analyses

The grades will be summarized using descriptive statistics and presented overall and for each age group and visit in total and by initial actual treatment group (placebo/dose level/overall active) on the OLS-300 for the analyzed OL-300 period.

9.8 CLINICAL LABORATORY TESTS

9.8.1 General

Clinical laboratory test results will be presented in Standard International (SI) units unless otherwise specified.

9.8.2 Double-blind Month 12 and OL-500 analyses

Clinical laboratory tests were summarized overall and for each age group, in total and by time point and treatment group (placebo/dose level/ overall active) for both absolute values and absolute changes from baseline on the SS for the randomized blinded treatment period.

These analyses were repeated overall and for each age group, in total and by time point and initial actual treatment on the OLS-500 for the Viaskin Milk 500 μ g open-label treatment period. Similarly, the last value in Viaskin Milk 500 μ g open-label treatment period should be summarized.

Shift tables were generated overall and for each age group, in total and by treatment group (placebo/dose level/overall active) of test abnormalities comparing baseline values to the values collected at Months 12.

Same analysis were performed overall and for each age group, in total and by initial actual treatment group of test abnormalities comparing baseline value (Month 0) to the last value in the Viaskin Milk 500 μ g open-label treatment period.

Listed data values that are outside the reference range were flagged (low or high), if applicable.

Urine pregnancy test results were listed only.

9.8.3 OL-300 Analyses

Clinical laboratory values will be summarized using descriptive statistics overall and for each age group, visit and time point in total and by initial actual treatment group (placebo/dose level/overall active) on the OLS-300.

This document is confidential

Statistical Analysis Plan

- Absolute values at Month 0, Month 12, last value prior to switch to Viaskin Milk 300 μ g and all scheduled visits in the analyzed OL-300 period
- Changes from last value prior to any active treatment
- Changes from last value prior to switch to Viaskin Milk 300 μ g

Listed data values that are outside the reference range were flagged (low or high), if applicable.

Urine pregnancy test results were listed only.

9.9 SPIROMETRY AND PEAK EXPIRATORY FLOW

9.9.1 General

Spirometry (FEV₁) and peak expiratory flow (PEV) will be assessed as absolute values and percentage relative to the predicted values.

Collected values will be listed.

9.9.2 Double-blind Month 12 and OL-500 analyses

FEV₁ and PEF results as % predicted values (actual values and change from baseline) were summarized overall and for each age group, visit and time point in total and by treatment group (placebo/dose level/ overall active) using descriptive statistics on the SS for the randomized blinded treatment period.

Same analysis was performed overall and for each age group, visit and time point in total and by initial actual treatment group on the OLS-500 for the Viaskin Milk 500 μ g open-label treatment period. Similarly, the last value in the Viaskin Milk 500 μ g open-label treatment period was summarized.

9.9.3 OL-300 Analyses

The following FEV₁ and PEF results as % predicted values will be summarized using descriptive statistics overall and for each age group, visit and time point in total and by initial actual treatment group (placebo/dose level/overall active) on the OLS-300.

- Absolute values at Month 0, Month 12, last value prior to switch to Viaskin Milk 300 μ g and all scheduled visits in the analyzed OL-300 period
- Changes from last value prior to any active treatment
- Changes from last value prior to switch to Viaskin Milk 300 μ g

This document is confidential

Statistical Analysis Plan

9.10 OTHER SAFETY

9.10.1 Body characteristics

9.10.1.1 General

Weight and height will be reported every six months during the study. From these the Body Mass index (BMI, kg/m²), Body Surface (m²), and weight/height (kg/m) will be derived.

9.10.1.2 Double-blind Month 12 and OL-500 analyses

Absolute values and changes from baseline were summarized overall and for each age group and visit, in total and by treatment group (placebo/dose level/overall active) as well as the respective derived values BMI (kg/m²), Body Surface (m²), and weight/height (kg/m) on the SS for the randomized blinded treatment period.

Same analyses were performed overall and for each age group and visit, in total and by initial actual treatment group, on the OLS-500 for the Viaskin Milk 500µg open-label treatment period, if applicable. Similarly, the last value in the Viaskin Milk 500µg open-label treatment period were summarized.

9.10.1.3 OL-300 Analyses

The following values will be summarized for weight, height, BMI, Body Surface and weight/height using descriptive statistics overall and for each age group, visit and time point in total and by initial actual treatment group (placebo/dose level/overall active) on the OLS-300.

- Absolute values at Month 0, Month 12, last value prior to switch to Viaskin Milk 300µg and all scheduled visits in the analyzed OL-300 period
- Changes from last value prior to any active treatment
- Changes from last value prior to switch to Viaskin Milk 300µg

9.10.2 Safety diary card data

Data derived from the diaries of the first 3 months of treatment were summarized overall and for each age group, in total and by actual treatment group (placebo/dose level/overall active) on the SS. This was done over the whole 3 months period and for 14-days intervals.

The number of days of itching, redness and swelling by severity was displayed. The most severe grades of itching, redness and swelling, documented in the diary card, were summarized. The maximum grade of local reaction reported (itching, redness or swelling) during the first 3 months was also tabulated.

The proportion of evaluations was tabulated by grade taken into account the maximum grade of itching, redness or swelling.

This document is confidential

Statistical Analysis Plan

After Month 3, these data are already collected and summarized as AE.

10 EXPLORATORY

10.1 EPIGENETIC MODIFICATIONS AT MONTHS 12, 24, 36 AND 48

Epigenetic analysis will be performed separately. Analysis details will not be described here.

10.2 FILAGGRIN GENE MUTATIONS

Filaggrin gene mutations was assessed from a blood sample collected at Screening and the results were summarized overall and for each age group, in total and by treatment group (placebo/dose level/overall active), whether no mutation, a heterozygous or a homozygous mutation was identified. Five different mutations are expected: R501X, 2282del4, R2447X, S3247X, 3702delG and will be included in the summary.

The relationship between the presence of filaggrin mutations (with/without), safety (SS) and response to treatment (ITT) was only investigated during the double-blind period (see [Section 8.1.7](#) and [9.2.2](#)).

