8.1.6.1.1 Sensitivity analyses on Primary efficacy criteria

Sensitivity analyses will be performed in order to evaluate the impact of the primary efficacy criteria to the results and interpretation of study results. The analysis described above will be repeated for subjects in the ITT using observed data and in the PPS. A similar analysis will be performed on ITT population using multiple imputation instead of missing = failure imputation method. Multiple imputation method will be further described in the SAP.

Other covariates of interest including baseline IgE (by levels) and country will be explored.

Finally, the primary efficacy analysis will be repeated for each age group as well as for each filaggrin mutation group (With filaggrin mutation / Without filaggrin mutation). Within subgroup, the treatment group comparisons will be conducted at a two-sided 10% significance level.

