8.1.8 Exploratory Variables

Exploratory endpoints include the change from baseline value in level of sIgE to peanut, egg, house dust mite, and grass pollen at all timepoints.

Exploratory endpoints will also include the change from baseline in epigenetic modifications at Month 12 and after Month 12 if evaluated.

The above analyses will be defined in the SAP.

Filaggrin gene mutations will be assessed from a blood sample collected at 1 visit and the results will be listed. The relationship between the presence of filaggrin mutations, safety and response to treatment will also be investigated. This analysis will be defined in the SAP.

Exploratory endpoints will also include the enumeration and characterization of reactions triggered by accidental consumption of cow's milk (in any form) and the analysis of "risk-taking behavior" of subjects (or voluntary milk consumption as assessed by the Investigators) during the study. Both pieces of information (accidental consumption and reactions triggered by consumption) will be collected from subject Diary Cards and voluntary or accidental consumption will be assessed by the investigative staff while interviewing the subjects.

Frequency of accidental consumption of cow's milk (in any form), conditions around the accidental consumption, estimated quantity consumed at each occurrence, and associated reactions and severity of reactions will be analyzed separately.

Risk-taking behaviors: frequency of deliberate consumption of cow's milk (in any form), conditions around the consumption, estimated quantity consumed at each occurrence and associated reactions with these consumptions will be analyzed separately. Relatedness to the subject's age category will also be analyzed.

End-of-study surveys completed by the investigators will be analyzed to assess the planned management of each subject after termination of the study.

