4.4 EXPLORATORY ENDPOINTS

- The change from baseline in epigenetic modifications at Month 12, if evaluated.
- Epigenetic modifications over the course of open-label treatment with Viaskin Milk 500 µg and 300 µg, if evaluated.
- The relationship between the presence of filaggrin mutations, safety, and response to treatment.
- The change from baseline value in levels of sIgE to peanut, egg, house dust mite, and grass pollen.
- Enumeration and characterization of reactions triggered by accidental consumption of cow's milk (in any form) during the study.
- Analysis of "risk-taking behaviour" of subjects (voluntary milk consumption) during the study.
- Planned management of the subject after termination of the study.

²Events are considered as systemic unless there is evidence in the event term or coding information that the reaction is only extended around the patch area.

Statistical Analysis Plan

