8.1.2 Primary efficacy analysis

Methods of exact logistic regression was used to compare the proportion of treatment responders at Month 12 in each dose level to placebo, adjusting for age group, and including the treatment group as fixed effect, for subjects in the ITT population.

P-values, Odds Ratios together with associated 95% Confidence Interval (CI) were presented. A SAS-Code similar to the following was used:

```
PROC LOGISTIC data=<inidata>;
  CLASS treat(ref="Placebo" param=ref) agegroup;
  MODEL y=treat agegroup;
  EXACT treat agegroup / estimate=both;
RUN;
```

Following analyses were performed by another CRO.

The primary analysis was performed using model-based analytical approaches which aim to inform the dose selection for phase 3. One of the methods to be used was the MCP-Mod method (Multiple Comparison Procedure – Modelling) [\[1\]](#) that included a first stage of hypothesis testing of candidate models to assess the presence of dose-response signal via a trend test (while preserving the family-wise error rate), and a second stage of dose-response modeling of the selected model to obtain inference on adequate doses.

This document is confidential

Statistical Analysis Plan

For the first stage of the MCP-Mod approach, the candidate model classes to be considered were linear, Emax, and logistic, but other candidate models were examined as well. More complex models such as sigmod and beta were considered. Prior to model comparison, exploratory analyses were performed in order to determine appropriate initial inputs for model parameters. The most adequate dose-response model within the candidate set was chosen as the one with the most significant contrast. For the second stage of the MCP-Mod approach, one or more candidate models were selected to provide inference on the adequate dose.

The success of this phase 2 study rested on identification of a viable dose, leading to design of a pivotal phase 3 trial.

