8.1.6 Sensitivity to (other) covariates

Efficacy endpoint analysis, as described in [section 8.1.2](#), was repeated for subjects in the ITT

- without adjusting for age group
- using country as covariate,
- using baseline cow's milk specific sIgE (categorized as in [section 7.1.2](#)) as covariate
- using filaggrin mutation subgroup (With/Without filaggrin mutation) as covariate
- using recruitment part (Part A/Part B)

These analyses were performed without adjusting for age group due to small sample sizes expected.

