8.1.7 Subgroup analyses

Efficacy endpoint analysis, as described in [sections 8.1.2](#), (and [8.1.3](#) for age subgroups only), were repeated for subjects in the ITT for the following subgroups:

This document is confidential

Statistical Analysis Plan

- each age groups (age group was not included as covariate; Newcombe confidence interval was not stratified on age group)
- each country (no covariate)
- baseline cow's milk specific IgE (categorized as in [section 7.1.2](#)) (no covariate)
- each filaggrin mutation subgroup (With/Without filaggrin mutation) (no covariate)

For descriptive purposes, 90%-CI were provided for the treatment comparisons.

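### The filaggrin-response endpoint has no treatment-by-filaggrin contrast, so the plan neither estimates nor tests whether the treatment effect differs by mutation status; age group has the same gap.

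*SAP*

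**What the plan says.** SAP 4.4 lists as an exploratory endpoint: "The relationship between the presence of filaggrin mutations, safety, and response to treatment". Protocol 8.1.8 leaves the method open: "This analysis will be defined in the SAP".

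The SAP contains two filaggrin analyses of response.

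- SAP 10.2 limits the question to the blinded year ("The relationship between the presence of filaggrin mutations (with/without), safety (SS) and response to treatment (ITT) was only investigated during the double-blind period") and points to SAP 8.1.7. There the analysis of SAP 8.1.2 is repeated for "each filaggrin mutation subgroup (With/Without filaggrin mutation) (no covariate". The base model is "MODEL y=treat agegroup": main effects only, with each dose compared with placebo.
- SAP 8.1.6 refits the whole-ITT model "using filaggrin mutation subgroup (With/Without filaggrin mutation) as covariate". SAP 10.2 does not cite this analysis.

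On inference, protocol 8.1.6.1.1 says of the age-group and filaggrin subgroups: "Within subgroup, the treatment group comparisons will be conducted at a two-sided 10% significance level". SAP 8.1.7 says: "For descriptive purposes, 90%-CI were provided for the treatment comparisons". SAP section 12, which lists departures from the protocol, does not withdraw the 10% rule. Age group is handled in the same way, with stratum-free Newcombe intervals for the risk difference added. No interaction term or heterogeneity test appears in the readable text.

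**The concern.** If the endpoint asks whether filaggrin status changes the response to treatment, the null hypothesis is that the dose effect is equal with and without a mutation. Each SAP 8.1.7 repeat tests a different null: that this dose has no effect within this subgroup. Two such p-values, or two separate intervals, do not estimate the difference between the subgroup effects. The SAP 8.1.6 covariate model assumes a common treatment effect, so it cannot show a difference either.

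Within-subgroup significance depends heavily on subgroup size. When one subgroup is much smaller, a dose with the same benefit in everyone can easily reach significance in the larger subgroup and miss it in the smaller one. The risk is that this pattern is read as filaggrin, or age, modifying the response.

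**Working it through.** **The plan's own figure.** There is none to reproduce, because the sample-size sections are blacked out.

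**Inputs from the documents.**

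- 198 subjects were randomised, 18 in Part A and 180 in Part B (SAP 3.1).
- Part A had three cohorts of 6 at 2:1, giving 4 per dose and 3 × 2 = 6 on placebo. Part B was 1:1:1:1, giving 180/4 = 45 per arm. Pooled, that is 4 + 45 = 49 per dose and 6 + 45 = 51 on placebo.
- The within-subgroup level is 0.10, two-sided (protocol 8.1.6.1.1).
- Missing response counts as non-response (SAP 8.1.1), so no dropout term is needed.

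**Assumed, not in the documents.** Carrier share, the fraction genotyped (genetic consent is optional, protocol 7.4) and response rates. True rates are set equal in carriers and non-carriers.

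**Discordance.** Let Pc and Pn be the probabilities that the dose-placebo test is significant in carriers and in non-carriers. They come from exact binomial enumeration of the two-sided Fisher test, which stands in for the exact logistic model without a covariate. Then

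P(exactly one significant) = Pc(1 − Pn) + Pn(1 − Pc).

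**Interaction test.** z = (ln ORc − ln ORn) / √(Vc + Vn), with 0.5 added to each cell, V the sum of reciprocal cell counts, and rejection at |z| > 1.645.

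Placebo 30%, dose 55%, everyone genotyped:

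| Carriers | Carrier n (dose v placebo) | Non-carrier n | Pc | Pn | Exactly one significant | Interaction rejects |
|---|---|---|---|---|---|---|
| 10% | 5 v 5 | 44 v 46 | 0.06 | 0.74 | 0.71 | 0.06 |
| 20% | 10 v 10 | 39 v 41 | 0.18 | 0.67 | 0.61 | 0.08 |
| 30% | 15 v 15 | 34 v 36 | 0.26 | 0.64 | 0.57 | 0.09 |
| 40% | 20 v 20 | 29 v 31 | 0.35 | 0.53 | 0.51 | 0.09 |

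For the 20% row: 0.181 × 0.333 + 0.667 × 0.819 = 0.060 + 0.546 = 0.606. So about 55% of such trials would show significance in non-carriers only, although the effect is identical.

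**Sensitivity to the assumptions.**

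- 10-point effect (30% v 40%): 0.22 to 0.23 over the same carrier shares.
- Very strong effect (10% v 60%): 0.78, 0.34, 0.16 and 0.05 at 10%, 20%, 30% and 40% carriers.
- No effect at all: 0.06 to 0.12 (10% to 50% carriers).
- 70% genotyped, 20-point effects: 0.38 to 0.61 (10% to 50% carriers).

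**Power of the interaction test.** Suppose the effect is lost completely in carriers (non-carriers 30% v 55%, carriers 30% v 30%). The test rejects in 16%, 25%, 30% and 32% of trials at 10%, 20%, 30% and 40% carriers. Pooling three equally effective doses (3 × 49 = 147 v 51) raises this to about 26%, 35%, 40% and 43%.

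No age split was calculated. For age group the point rests on the missing contrast alone.

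**The case against.** The strongest case against has five parts.

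- **The covariate model exists.** A reader might infer that the subgroup repeats are the only filaggrin analysis. They are not, because SAP 8.1.6 fits filaggrin across the whole ITT. If the endpoint's word relationship means association with responder status, that model addresses it. This stands as far as it goes, but the model cannot show whether the treatment effect differs.
- **The intervals are labelled descriptive, and no rule says that significance in one subgroup alone means a filaggrin effect.** This is correct. A reader might infer that the plan will usually produce a false filaggrin finding. The documents do not support that: the misreading depends on whoever reads the tables, and the discordance rate depends on quantities they do not give. Still, the protocol's 10% tests have not been withdrawn, and the descriptive label does not supply the missing estimate.
- **Multiplying over doses exaggerates.** Counting any discordant dose of three gives 82% to 98% in simulations with 10% to 30% carriers. That assumes three equally effective doses, whereas protocol 3.1 reports 300 µg as the most effective. The per-dose figures are the ones to use.
- **The remedy is weak.** The power figures above confirm it.
- **The analysis is done.** SAP 11.1 records that the Month 12 database was locked, unblinded and reported under SAP version 4.0. A contrast added now is post hoc, and rewording the protocol cannot change what was run.

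**Conclusion.** The point holds in a limited form. Under the reading that response to treatment may depend on filaggrin status, no specified analysis estimates or tests that dependence, and the same is true for age group. This follows from the text and needs no assumption about rates.

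How misleading the subgroup results could be does depend on assumptions. With 30% versus 55% and 10% to 40% carriers, an identical effect gives exactly one significant subgroup in about 51% to 71% of trials per dose, against about 6% to 9% rejections for a direct interaction test. The discordance is about 22% for a 10-point effect and can fall to about 5% for a very strong effect with 40% carriers. The supportable statement is that unequal subgroup sizes can often make an identical effect look different.

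The endpoint is exploratory, and the documents tie no primary or dose-selection conclusion to it. This is a worthwhile, inexpensive improvement and does not threaten the main result.

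**What to change.** In SAP 8.1.7 and 10.2:

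1. Add a logistic model with treatment, filaggrin status and their interaction. Report the ratio of odds ratios, or the difference between the subgroup risk differences, with a 90% interval. Pool the active doses against placebo if carriers are few.
2. Do the same for age group.
3. Label these estimates exploratory and, because Month 12 is already unblinded, post hoc.
4. Keep the within-subgroup estimates and 90% intervals as description only. State that no subgroup difference is inferred from significance in one subgroup and not in the other.
5. While editing SAP 10.2, correct its safety cross-reference. Section 9.2.2 covers treatment compliance; the filaggrin overviews of adverse events are in 9.3.3.1.

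The cost is SAP wording and one extra model per factor on data already collected. The result can go into the final study report, which covers the whole study (protocol 3.1). The drawback is an imprecise estimate with low power even for complete loss of effect in carriers, so the text should say that a non-significant interaction is not evidence of a uniform effect.

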10.3 ADDITIONAL IMMUNOLOGICAL MARKERS

10.3.1 General

Immunological markers are also available for Peanut, Egg White, House Dust Mite and Grass Pollen.

10.3.2 Double-blind Month 12 and OL-500 analyses

Actual values and changes from baseline for the additional immunological markers were summarized overall and for each age group, in total and by treatment group (placebo/dose level/overall active), for each time point until Month 12 for the randomized blinded treatment period in the ITT.

Same analyses were repeated overall and for each age group, in total and by initial randomized treatment group on the OLS-500 for each time point of the Viaskin Milk 500µg open-label treatment period. Similarly, the last value in the Viaskin Milk 500µg open-label treatment period were summarized.

Repeated-measures ANCOVA models were built to compare the mean absolute change from baseline value (Visit 1) during the randomized blinded treatment period in

- 1) Specific IgE Peanut
- 2) Specific IgE Egg White
- 3) Specific IgE House Dust Mite D. Pter
- 4) Specific IgE Timothy Grass Pollen

This document is confidential

Statistical Analysis Plan

similar to the analysis of the immunological markers ([Section 8.2.3](#)).

The distribution of each parameter was examined graphically (Bar-Chart) a natural log transformation of the data was performed to be used in the analysis.

These ANCOVA models were not repeated for open-label time points.

